4. STUDY DESIGN

4.1. Study Design

This is a Phase 3b, multicenter, double-blind, parallel group, randomized extension study that will evaluate the efficacy and safety of 2 treatment regimens of edaravone for an additional period of up to 48 weeks following Study MT-1186-A02 in subjects with ALS as follows:

- Group 1: Oral edaravone 105 mg dose once daily for up to 48 weeks or until the drug is commercially available in that country.
- Group 2: Oral edaravone 105 mg dose for 10 days followed by 18-day placebo (regimen denoted as on/off) for up to 48 weeks or until the drug is commercially available in that country.

Subjects who meet study MT-1186-A04 eligibility criteria, will continue in the same treatment group/regimen which they were allocated to in during Study MT-1186-A02.

The Week 48 study procedures from Study MT-1186-A02 will be used as the screening/entry criteria for Study MT-1186-A04, followed by a treatment period of up to an additional 48 weeks or until oral edaravone is commercially available in each country, whichever time period is shorter, and a safety follow-up period of 2 weeks.

During the conduct of Study MT-1186-A04, the dose of edaravone may be adjusted or the study may be stopped based on the interim futility or final analyses performed for Study MT-1186-A02, taking into consideration the benefit and risk balance. However, unless any significant safety issue is found based on these 2 analyses, the same regimen will be kept while maintaining the blind conditions for all site-facing personnel and all personnel directly involved with the conduct of the study.

[During the conduct of Study MT-1186-A02 and Study MT-1186-A04]

Before this SAP version 1.0 was finalized and signed, a futility analysis was performed for Study MT-1186-A02. Following this futility analysis, the IDMC recommendation was to stop MT-1186-A02 study. As a result and taking the pre-planned options regarding MT-1186-A04, the sponsor endorsed the IDMC recommendation and decided also to terminate the MT-1186-A04 study.

Concomitant use of riluzole is permitted throughout the course of the study when the dose and regimen remain unchanged from the Day 1/screening visit evaluation of ALSFRS-R of Study MT-1186-A02 through the end-of-treatment (EOT) or early termination (ET) of Study MT-1186-A04. Dose reduction, dose interruption, or discontinuation due to the onset of AEs, progression of dysphagia, or gastrostomy while on oral edaravone 105 mg are allowed. The use of AMX0035 will be allowed for patients in the event that it becomes commercially available via

Mitsubishi Tanabe Pharma America, Inc.

prescription in their respective country. AMX0035 should be taken at least 1 hour after MT-1186/oral edaravone dosing.

[figure not shown]
EOT assessments will occur at Week 48 (Visit 5). For subjects who complete the double-blind treatment period, a safety follow-up telephone visit will occur at Week 50 (Visit 6).

Subjects will be allowed to change from oral administration to PEG/RIG tube administration during the study. Subjects who discontinue early from the study will complete the procedures listed at Week 48 within 7 days of discontinuation.

Site staff should also follow up via phone call at all remaining visits to complete the assessment for time to tracheostomy or permanent assisted mechanical ventilation, or death.

Further details can be found in the Study Schema (Figure 1). The schedules of assessment for each country specific (Japan) are referred to each country specific protocol.

Figure 1: Study Schema

Abbreviation: EOS = end-of-study; EOT = end-of-treatment: ET = early termination.

Day 1 is equal to the Week 48 visit of Study MT-1186-A02.

a. Subjects will receive or al edaravone at a dose of 105 mg administered once daily in each 28 Day Cycle or a dose of 105 mg administered for 10 days, followed by placebo for 18 days in each 28 Day Cycle. The dose of edaravone should be taken following an overnight fast and at least 1 to 2 hours before the morning meal.

Mitsubishi Tanabe Pharma America, Inc.

Statistical Analysis Plan Study No. MT-1186-A04 Table 1: Schedule of Activities

Assessment						
Week (window)	Dav 1	12	ੜ	36	8†	90
,	(Based on Week 48	(± 7D)	(± 7D)	(± 7D)	(± 7D)	(± 7D) Telephone Visit
	procedures from Study MT-1186-A02)	Telephone Visit		Telephone Visit	EOT/ET	EOS
Cicle	1	†	7	10		
Visit	1	č	3	t	w	9
Informed consent	Х					
Eligibility criteria	Х					
Demographics	x					
Vital signs ^c	Х		X		х	
Full Physical examination ^d	X				×	
Routine physical examination ⁴			×			
12-lead ECG*	Х		Х		х	
Body weight	Х		Х		Х	
Time to event of death, tracheostomy or permanent assisted mechanical ventilation	x	Х	X	X	×	×
Hematology®	×		×		x	
Chemistry≥	×		х		X	
Urinalysisi	Х		Х		×	
Serum Pregnancy Test (WOCP only)	х		X		х	
Urine Pregnancy Test (WOCP only)	Х					
Dispense edaravone k	×		x			
ALSFRS-R	х	x	X	х	×	
ALSAQ40	Х		X		×	·
Slow Vital Capacity	х		х		x	
C-SSRS	х		x		×	
Adverse events	х	Х	Х	х	Х	X

Page 14 of 61

Study No. MT-1186-A04 Statistical Analysis Plan

Mitsubishi Tanabe Pharma America, Inc.

Assessment						
Week (window)	Day 1 (Based on Week 48 procedures from	12 (± 7D)	24 (± 7D)	36 (± 7D)	±8 (±.7D)	\$0 (± 7D) Telephone Visit
	Study MT-1186-A02)	reepnone visit		retephone visit	E01/E1	FOS
Cycle	1	+	7	10		
Visit	1	c1	3	+	w.	9
Concomitant medications	х	Х	Х	×	×	X
Medication Compliance Assessment ¹	х	х	х	Х	X	

Abbreviation: AE = adverse event; ALSAQ = Amyotrophic Lateral Sclerosis Assessment Questionnaire; ALSFRS-R = Revised Amyotrophic Lateral Sclerosis Functional Rating Scale; D = Day, ECG = Electrocardiogram; EOS = End-of-study; EOT = End-of-treatment; ET = Early Termination; WOCP = women of childbearing potential.

Subjects who withdraw from the study will complete the procedures listed in ET within 7 days of study discontinuation.

Demographics will include age, sex, race, and ethnicity

Vital signs will include sitting systolic and diastolic blood pressure, heart rate, respiratory rate, and axillary, oral, temporal (skin-based), or tympanic body temperature.

Physical examination:

1. A full physical examination will consist of an assessment of the major body parts and systems: abdominal, cardiovascular, general appearance, head, eyes. ears/nose/throat, lymph nodes, musculoskeletal, neck, neurological, dermatological, respiratory, and other.

Routine physical examination will include abdominal, cardiovascular, general appearance, respiratory, neurological, and other.

A 12-lead ECG will be performed after the subject has rested for at least 5 minutes in a supine position. The ECG must include the following measurements: R wave to Investigator will perform an overall evaluation of the ECG for safety purposes and the recording will be reported as 'normal', 'abnormal clinically significant (CS)', or 'abnormal not clinically significant (NCS)'. Abnormalities of clinical significance will be reported as AEs. R wave (RR) interval, heart rate, QRS, and QT. If available, corrected QT interval by Bazett, and corrected QT interval by Fridericia should also be recorded. The نه

Events are time to death, tracheostomy, or permanent assisted mechanical ventilation (>23 hours/day). If a subject discontinues early from the study, study sites must follow-up with phone calls at all remaining visits. 4

To include: red blood cell count, hemoglobin, hematocrit value, white blood cell count with differential, and platelet count.

c-reactive protein, creatine kinase, total cholesterol, triglycerides, blood urea nitrogen, bicarbonate, serum glucose, serum creatinme level, uric acid, sodium, potassium, To include: albumin, total protein, aspartate aminotransferase, alanine aminotransferase, lactate dehydrogenase, alkaline phosphatase, total bilirubin, direct bilirubin, chloride, calcium, cystatin-C, and vitamin B6 بعر بنه

To include protein, glucose, occult blood, urobilinogen, white blood cells, and bilirubin.

For female subjects of childbearing potential (WOCP) only, urine beta-human chorionic gonadorropin test will be conducted.

olacebo for 18 days (regimen denoted as on/off) in Cycles 1 through 12, following an overnight fast, and subjects must continue to fast at least 1 to 2 hours post-dose Subjects will receive oral edaravone 105 mg once daily in each 28 Day Cycle (Cycles 1 through 12) or oral edaravone 105 mg administered for 10 days followed by before the next meal (e.g., breakfast)

Screening/Day 1 drug compliance should be assessed as part of Study MT-1186-A02/Week 48 visit. Once a subject is eligible to enroll in Study MT-1186-A04, drug compliance should be assessed on a per cycle basis by site staff via study phone calls (Weeks 12 and 36) or during the in-clinic visits.

Mitsubishi Tanabe Pharma America, Inc.

4.2. Sample Size and Power Considerations

In total, approximately 300 subjects who have successfully completed Study MT-1186-A02 are anticipated to be enrolled in this MT-1186-A04 study. A formal sample size calculation was not performed. However, data from 380 subjects (190 subjects per group) randomized in Study MT-1186-A02 will be included for all analyses. Hence, using MT-1186-A02 and MT-1186-A04 survival data and assuming 65% survival rate of the primary endpoint for the control group, the planned sample size of 190 subjects per group initially randomized in Study MT-1186-A02 will provide 70% power to detect a statistically significant result if the true hazard ratio between edaravone 105 mg daily (test) and edaravone 105 mg on/off regimen (control) in the primary endpoint is HR=0.775 (implying 22.5% risk reduction in the hazard due to daily treatment). This calculation of 70% power assumes a 2-sided alpha of 20% based on a rare disease condition (Hilgers RD et al., 201614) using the log-rank test and a follow-up time of up to 48 weeks in Study MT-1186-A04.

When this SAP version 1.0 was finalized and signed, for 384 subjects randomized in Study MT-1186-A02, 202 subjects who have successfully completed Study MT-1186-A02 were enrolled in this MT-1186-A04 study.

5. PLANNED ANALYSIS

5.1. Interim Analysis

Interim Data Lock and Interim Analysis will take place when the last subject randomized in Study MT-1186-A02 completes the last visit in that study. At this time point, data-lock will combine data collected up to the Week 48 visit in Study MT-1186-A02 with data collected from the current Study of MT-1186-A04. The timing of Study MT-1186-A04 data lock will be approximately at the same time as of MT-1186-A02 final data lock.

[During of Conducting Study MT-1186-A02 and MT-1186-A04]

Before this SAP version 1.0 was finalized and signed, a futility analysis has been already performed for Study MT-1186-A02. Following this futility analysis, the IDMC recommendation was to stop MT-1186-A02 and MT-1186-A04 study. The sponsor endorsed the IDMC recommendation and as a result, the timing of the above interim analysis for MT-1186-A04 study will include all data accumulated until the MT-1186-A02 cessation.

Unblinding for Study MT-1186-A04 due to MT-1186-A02 Final Analysis

The MT-1186-A02 study results will not be disclosed to any site-facing personnel or to any personnel directly involved with the conduct of Study MT-1186-A04. This procedure was

Mitsubishi Tanabe Pharma America, Inc.

prespecified in MT-1186 A02 Unblinded Data Access Plan and Communication Rules as Note to File.

5.2. Final Analysis

Final Data Lock and Final Analysis will take place when the last subject completes the Week 50 visit or the safety follow up period of Study MT-1186-A04. The analysis undertaken for Study MT-1186-A04 will include data from baseline of Study MT-1186-A02 until the end of Study MT-1186-A04. The data will also include information for subjects who early terminated during Study MT-1186-A02 or decided not to continue into Study MT-1186-A04. All analyses performed following the final data lock will be specified in this SAP. Additional analysis may be performed if deemed necessary.

[During of Conducting Study MT-1186-A02 and MT-1186-A04]

As mentioned in above, due to futility analysis performed for Study MT-1186-A02 and the sponsor decision to stop both MT-1186-A02 and MT-1186-A04, final analysis for MT-1186-A04 study will not be conducted.

5.3. Data Monitoring Committee (DMC)

An Independent Data Monitoring Committee (IDMC) is a multidisciplinary group comprised of medical/clinical experts and a biostatistician, all external to the sponsor. The same IDMC appointed for MT-1186-A02 will continue to review unblinded safety data periodically for the current study, at predefined intervals. The data for review will combine the MT-1186-A02 and MT-1186-A04 database. Any such reviews of study data will be undertaken in accordance with predefined rules and procedures. These rules will be implemented to ensure that access to details of the study blind, and to unblinded data, is carefully controlled.

A charter will guide the timing of reviews, communications between the IDMC, the Investigators, and the Sponsor, and stopping rules for the study. In general, the IDMC will advise the Sponsor regarding possible changes to the protocol or study procedures to protect the subjects enrolled in the study.

[During of Conducting Study MT-1186-A02 and MT-1186-A04]

Following a futility analysis performed MT-1186-A02, the IDMC recommendation was to stop MT-1186-A02 study. As a result, the sponsor decision was to stop both MT-1186-A02 and MT-1186-A04.

Mitsubishi Tanabe Pharma America, Inc.

6. ANALYSIS POPULATIONS

The statistical analysis will be based on separate analysis sets, defined as follows:

6.1.1. Randomized Set

The randomized set is defined as all of the subjects randomized in Study MT-1186-A02. The subjects will be grouped by the planned treatment allocation (as randomized).

6.1.2. Efficacy Full Analysis Set (FAS)

The full analysis set (FAS) is defined as all of the subjects randomized in Study MT-1186-A02 who received at least 1 dose of study medication in Study MT-1186-A02. Subjects in the FAS will be grouped and analyzed based on the planned treatment allocated (as randomized). Efficacy endpoints will be analyzed using the FAS.

6.1.3. Safety Analysis Set (SAF)

The Safety Analyses Set (SAF) is defined as all of the subjects randomized in Study MT-1186-A02, and who received at least 1 dose of study drug in Study MT-1186-A02. Subjects will be grouped and analyzed based on the actual treatment received. Safety endpoints will be analyzed using the SAF by treatment group.

7. STATISTICAL CONSIDERATIONS

7.1. Descriptive Statistics

Data listings will be sorted by center and subject number (and by visit, if applicable). Continuous data will be summarized descriptively using the number in the analysis set (N), the number of observations (n), mean, standard deviation (SD), median, minimum and maximum. Categorical data will be summarized using frequency counts and percentages. The denominator for the percentages will be the total number of subjects in the treatment group and analysis set being presented, unless otherwise specified. For visit-specific data, the number of subjects with non-missing observations at the visit in question will be used as the denominator for percent calculations. Unknown, Not Done, Not Applicable and other classifications of missing data will not be considered.

7.2. Type I Error Control

Type I error will not be controlled for multiplicity adjustment between the primary endpoint and the secondary endpoints. All statistical tests for primary endpoint as well as for other endpoints will be done at 2-sided significance level with nominal values of 20% and 5%,

Mitsubishi Tanabe Pharma America, Inc.

respectively. Point estimates of treatment differences will be accompanied with 2-sided 80% and 95% confidence intervals where applicable respectively.

8. DATA CONVENTIONS

8.1. Baseline Definition

In general, Baseline will be defined for each subject as the last available, valid, non-missing assessment obtained prior to the first date of study drug administration. The data collected before the first study drug dose administration date in Study MT-1186-A02 will be used as the baseline for statistical analysis in the current MT-1186-A04 Study.

8.2. Data Handling Convention for Missing Data

In general efficacy data will not be imputed unless otherwise noted. For safety summaries, only observed data will be used. Unless otherwise specified, missing safety data will not be imputed. For each analysis variable, how to handle missing data are described in section 8.3 respectively.

8.3. Analysis Variable Definitions

8.3.1. Study Subjects Measures

8.3.1.1. Protocol Deviation

Protocol deviations which occurred during Study MT-1186-A04 will be identified, confirmed and documented during a blinded data review meeting prior to database lock in Study MT-1186-A04. The major protocol deviations will be selected and identified prior to database lock in a blinded review meeting, including the following bullet points:

- Inclusion/Exclusion criteria violation in Study MT-1186-A04
- Taking prohibited concomitant medications except for AMX0035
- Test/Procedure/Scales (ALSFRS-R, ALSAQ-40 or C-SSRS performed by non-certified staff/rater

8.3.1.2. Demographic and Other Baseline Characteristics

8.3.1.2.1. Demographics:

This data not collected in MT-1186-A04 will be taken from MT-1186-A02.

Continuous: age, height, weight, Body Mass Index (BMI);

Categorical: age categorized as \leq 64 years versus \geq 65 years, and \leq 19, 20–29, 30–39, 40–49,

Mitsubishi Tanabe Pharma America, Inc.

50–59, 60–69, ≥ 70, gender, race, ethnicity, country and region defined as America- AM, Europe -EU and Asia Pacific - AP

O BMI will be calculated as weight at screening (kg) / {height at screening (m)}² and reported to 1dp.

Table 2: Demographic and Baseline Characteristics

Category	Item	Type of Data	Definition/Breakdown
	Gender	Binary	Male, Female
	Race	Categorized	 White Black or African American Asian – Japanese Asian - Not Japanese American Indian or Alaska Native Native Hawaiian or Pacific Islander Not Reported Other
Demography		Continuous	
	Age (year)	Categorized	\leq 19, 20–29, 30–39, 40–49, 50–59, 60–69, \geq 70
		Categorized (binary)	<65, ≥ 65
	Height (cm)	Continuous	
	Body weight (kg)	Continuous	
	BMI	Continuous	Weight at screening (kg) / {height at screening (m)} ²
	Country	Categorized	United States, Canada, Germany,
			Italy, Switzerland, Japan, South
			Korea
	Region	Categorized	1. America-AM
	•		2. Europe -EU
			3. Asia Pacific - AP
	Ethnicity	Categorized	1. Hispanic or Latino
			2. Not Hispanic or Latino
			3. Not Reported
			4. Unknown

Mitsubishi Tanabe Pharma America, Inc.

8.3.1.2.2. ALS History:

This data not collected in MT-1186-A04 will be taken from MT-1186-A02.

Continuous:

- (1) Disease Duration from Onset of Symptoms (years) and from ALS Diagnosis (years),
- (2) ALSFRS-R score at screening,
- (3) ALSFRS-R at Baseline,

Categorical:

- (1) ALSFRS-R Deterioration Rate of (-1,-2) or (-3,-4),
- (2) Disease duration from Onset of Symptoms categorized at <1 year vs ≥ 1 year and from Onset of ALS Diagnosis categorized at <1 year vs ≥ 1 year,
- (3) Initial symptom categorized as 'Bulbar onset' or 'Limb onset',
- (4) ALS Diagnosis categorized 'Sporadic' or 'Familial',
- (5) Categorical El Escorial revised Diagnostic,
- (6) Concomitant use of riluzole 'Present' or 'Absent',
- (7) Previous use of AMX0035 'Present' or 'Absent',
- (8) Concomitant use of AMX0035 'Present' or 'Absent',

Table 3: ALS History Parameters

Category	Item	Type of Data	Definition/Breakdown
	Disease duration from Onset of	Continuous	(Date of Screening - Date of Onset of Symptoms*)/365.25
	Symptoms to Screening (year)	Categorized (binary)	< 1 year, ≥ 1 year
	Disease duration from Diagnosis to	Continuous	(Date of Screening - Date of Diagnosis*)/365.25
AT G D:	Screening (year)	Categorized (binary)	< 1 year, ≥ 1 year
ALS Disease History	ALSFRS-R score at screening	Continuous	At Screening
	ALSFRS-R score at baseline	Continuous	At Baseline
	ALSFRS-R Deterioration Rate	Categorized	(-1,-2), (-3,-4)
	Initial symptom	Binary	Bulbar onset, limb onset
	ALS diagnosis	Binary	Sporadic, Familial

Mitsubishi Tanabe Pharma America, Inc.

	El Escorial revised	Binary	Definite ALS, Probable ALS,
	Airlie House		
	Diagnostic Criteria		
	Concomitant use of	Binary	Present, Absent
	riluzole		
	Previous use of	Binary	Present, Absent
	AMX0035		
	Concomitant use of	Binary	Present, Absent
	AMX0035		

^{*}If Date of Onset of Symptoms and Date of Diagnosis are incomplete, the following steps will be considered. If the above date is completely missing, the corresponding duration will not be derived. If the start month is missing, then the first month will be used. If the start day is missing, then the first day will be used.

8.3.1.3. Concomitant Medication

Definition of concomitant medications in the protocol

Concomitant medication is defined as any medication, other than the study drug, which is taken after the first dose administration in Study MT-1186-A02, including prescription, herbal and over-the-counter medications. All concomitant medications taken while the subject is participating in the study will be recorded in the eCRF. All medications will be classified using the Anatomical Therapeutic Chemical (ATC) classification codes and preferred drug names from the World Health Organization Drug Dictionary (WHO-DD, version from September 2019).

Concomitant medications, except for riluzole, will be summarized by ATC level 2 categories and preferred name. Riluzole administration will be summarized separately.

Rules to determine concomitant medications

Medications with a stop date before the first date of study drug dosing in MT-1186-A02 will be considered prior medications. Medications with start date or stop date on or after the first date of study drug dosing in MT-1186-A02 or ongoing up to week 48 in MT-1186-A04 will be considered concomitant medications.

If the medication start date is incomplete, then it will be imputed as follows for the purpose of determining concomitant use:

• If the start date is completely missing, the start date will be equal to the first dose date.

However, if the stop date is not missing and is before the first dose date, then the stop date will be used instead.

Mitsubishi Tanabe Pharma America, Inc.

- If the start day is missing, the first day of the month will be used.
- If the start day and month are missing, then the first day of the first month (January) will be used.

If the medication stop date is partial, then it will be imputed as follows for the purpose of determining concomitant use:

- If the stop date is completely missing and the medication is not ongoing, the stop date will be equal to the last dose date or date of completion/withdrawal, whichever is the latest.
- If the stop day is missing, the last day of the month will be used.
- If the stop day and month are missing, then the last day of the last month (December) will be used.

Integration of continued concomitant medications from MT-1186-A02 to MT-1186-A04:

All concomitant medications form MT-1186-A02 will be combined to concomitant medications captured in the MT-1186-A04 study in order to analyze the continued concomitant medication profile. If concomitant medication (CM) in MT-1186-A04 met all following conditions, the CM in MT-1186-A02 and MT-1186-A04 will be merged to a single CM.

- Start date of CM in MT-1186-A02 = Start date of CM in MT-1186-A04
- ATC2 name derived from medication term of CM in MT-1186-A02 = ATC2 name derived from medication term of CM in MT-1186-A04
- "Was this medication ongoing at the end of MT-1186-A02?" in MT-1186-A04 CRF = "Yes"
- "End date" = "Ongoing" in MT-1186-A02 CRF

Then, for CM analysis, CM End date in MT-1186-A04 CRF data rather than MT-1186-A02 CRF data will be prioritized and analyzed.

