8 STUDY DESIGN

8.1 Overall Study Design

This is a Phase 3b, multicenter, double-blind, parallel group, randomized extension study that will evaluate the efficacy and safety of 2 treatment regimens of edaravone for an additional period of up to 48 weeks following Study MT-1186-A02 in subjects with ALS as follows:

- Group 1: Oral edaravone 105 mg dose once daily in each 28-day cycle for up to 48 weeks or until the drug is commercially available in that country.
- Group 2: Oral edaravone 105 mg dose for 10 days followed by 18-day placebo (regimen denoted as on/off) in each 28-day cycle for up to 48 weeks or until the drug is commercially available in that country.

Subjects who meet study MT-1186-A04 eligibility criteria, will continue in the same treatment group/regimen that they were in during Study MT-1186-A02.

A schedule of assessment of all study procedures is provided in Table 1.

The Week 48 study procedures from Study MT-1186-A02 will be used as the screening/entry criteria for Study MT-1186-A04, followed by a treatment period of up to an additional 48 weeks or until oral edaravone is commercially available in each country, whichever time period is shorter, and a safety follow-up period of 2 weeks.

During the conduct of Study MT-1186-A04, the dose of edaravone may be adjusted or the study may be stopped based on the interim futility or final analyses performed for Study MT-1186-A02, taking into consideration the benefit and risk balance. However, unless any significant safety issue is found based on these 2 analyses, the same regimen will be kept while maintaining the blind conditions for all site-facing personnel and all personnel directly involved with the conduct of the study.

Concomitant use of riluzole is permitted throughout the course of the study when the dose and regimen remain unchanged from the screening visit evaluation of ALSFRS-R of Study MT-1186-A02 through the end-of-treatment (EOT) or early termination (ET) of Study MT-1186-A04. Dose reduction, dose interruption, or discontinuation due to the onset of AEs, progression of dysphagia, or gastrostomy while on oral edaravone 105 mg are allowed. The use of AMX0035 will be allowed for patients in the event that it becomes commercially available via prescription in their respective country. AMX0035 should be taken at least 1 hour after MT-1186/oral edaravone dosing.

EOT assessments will occur at Week 48 (Visit 5).

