8.3.3. Safety Measures

8.3.3.1. Adverse Events

An AE is any untoward medical occurrence in a subject or clinical investigation subject administered a pharmaceutical product that does not necessarily have a causal relationship with this IMP. An AE can therefore be any unfavorable and unintended sign (including an abnormal laboratory finding, for example), symptom, or disease temporally associated with the use of an IMP, whether or not considered related to the IMP.

Adverse events will be coded according to the MedDRA version 23.0

- Adverse Events will be classified for Treatment Emergent AEs (TEAEs) if at least one of the following conditions is met:
 - The AE was not present before the first dose in Study MT-1186-A02 but started after administration of the first dose of study drug in Study MT-1186-A02, or,
 - The AE was present before the first dose in Study MT-1186-A02 but increased in severity following administration of the first dose of study drug in Study MT-1186-A02.

Mitsubishi Tanabe Pharma America, Inc.

Integration of continued AEs from MT-1186-A02 to MT-1186-A04:

TEAE's from MT-1186-A02 will be integrated into TEAE's from the current MT-1186-A04 study in order to be able to analyze the continued safety profile. If AE in MT-1186-A04 met all following conditions, the AE in MT-1186-A02 and MT-1186-A04 will be merged into a single AE.

- Onset date of AE in MT-1186-A02 = Onset date of AE in MT-1186-A04
- Lowest level terms (LLT) of AE in MT-1186-A02 = LLT of AE in MT-1186-A04
- "Was this event ongoing at the end of MT-1186-A02?" in MT-1186-A04 CRF = "Yes" Then, for AE analysis, AE End date and Outcome data in MT-1186-A04 CRF data rather than MT-1186-A02 CRF data will be prioritized and analyzed.

Handling Partial Dates:

The handling of partial dates in study MT-1186-A02 were provided in a designated SAP for this study. The following are the rules for partial dates handling for TEAE's newly captured in MT-1186-A04 study:

- AE with a missing start time, but with a start date equal to the date of first dose of study treatment in MT-1186-A04 will be considered treatment-emergent.
- If the AE start date is incomplete, it will be imputed as follows for the purpose of determining TEAE:

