9.1.6. Concomitant Medications

All concomitant medications taken during only MT-1186-A04 will be listed and those occurred during MT-1186-A02 and MT-1186-A04 summarized by treatment group for the FAS. Separate summaries of permitted concomitant medications, (riluzole and AMX0035), will be presented in tabular form using the ATC Level 4 and preferred term. Other concomitant medications will be presented in tabular form using the ATC Level 1, ATC Level 2, and PT. Frequencies and percentages of subjects receiving medications will be presented. The tables will be sorted by overall descending frequency of ATC Level(s) and then, within an ATC Level, by overall descending frequency of PT.

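### SAP 8.3.1.3 merges A02 and A04 medication records with no drug-level match, so two continuing drugs in one ATC level 2 group with the same start date can be confused

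*SAP*

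**What the plan says.** SAP section 8.3.1.3, in its part on medications continued from A02 into A04, merges two records into one when four conditions all hold:

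1. "Start date of CM in MT-1186-A02 = Start date of CM in MT-1186-A04".
2. "ATC2 name derived from medication term of CM in MT-1186-A02 = ATC2 name derived from medication term of CM in MT-1186-A04".
3. The A04 form flags the drug as ongoing when A02 ended.
4. The A02 form gives the end date as ongoing.

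The A04 end date is then used. The section does not say which drug name the merged record carries, or what happens when one record matches several.

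The same section imputes incomplete start dates, for the stated purpose of deciding whether use was concomitant: "If the start date is completely missing, the start date will be equal to the first dose date", unless a known stop date is earlier. A missing day becomes the first of the month, and a missing day and month become 1 January. Coding uses the September 2019 version of WHO-DD.

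Reporting is finer than the merge key. Under SAP section 9.1.6, riluzole and AMX0035 "will be presented in tabular form using the ATC Level 4 and preferred term", and other drugs are shown by ATC level 1, ATC level 2 and preferred term. The tables hold numbers and percentages of subjects.

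The parallel rule for adverse events in SAP section 8.3.3.1 matches at the most specific coding level: "Lowest level terms (LLT) of AE in MT-1186-A02 = LLT of AE in MT-1186-A04".

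**The concern.** A rule that decides whether two records are the same drug should contain something that identifies the drug. This one does not. The two ongoing conditions restrict it to drugs carried over from A02, but they cannot tell one carried-over drug from another. That leaves start date and therapeutic group, and two drugs from one group begun on the same day agree on both.

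Where that happens, the SAP leaves the result to the programmer. Depending on how multiple matches are resolved, one drug may disappear under the other's name or take the other's end date. Two programmers following the text could produce different preferred-term tables. The plan already has a better pattern in its adverse event rule, and the finer level of its own medication tables requires one. SAP section 5.2 says no final analysis will be run, so the combined A02/A04 interim analysis is the one in which this has to be right.

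**Working it through.** The plan states no figure on this point, so there is none to reproduce. The check applies the four conditions literally to hypothetical records.

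**Inputs.** The four conditions come from SAP 8.3.1.3. Take two drugs, A and B, in one subject. Each has an A02 record and, if continued, an A04 record. The last column adds equality of preferred name to the key.

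| Case | A02–A04 pairs under the SAP rule | Separate records if all matches are linked | With preferred name added |
|---|---|---|---|
| Same ATC2, same start date, both continue | 4 (A–A, A–B, B–A, B–B) | 1 | 2 pairs, 2 records |
| Same ATC2, different start dates | 2 (A–A, B–B) | 2 | 2 pairs, 2 records |
| Different ATC2, same start date | 2 (A–A, B–B) | 2 | 2 pairs, 2 records |
| Same ATC2, same start date, B stopped in A02 | 1 (A–A) | 2 | 1 pair, 2 records |

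Only the first case fails. In general, k continuing drugs that share ATC2 and start date give k × k matching pairs where k are correct: 4 against 2 for k = 2, and 9 against 3 for k = 3.

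**Effect on the tables.** In the first case the subject should count once in row A, once in row B, and once in the common ATC level 2 and level 1 rows. If only the name A survives, the counts become:

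- preferred-term row B: 1 − 1 = 0;
- preferred-term row A: 1, unchanged;
- ATC level 2 row: 1, unchanged, because A and B share it;
- ATC level 1 row: 1, unchanged for the same reason.

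A wrong end date changes the integrated record but no table planned in SAP 9.1.6, which shows no durations. A drug still ongoing at the end of A02 is concomitant under SAP 8.3.1.3 whatever its later end date.

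**Effect on AMX0035, the first intercurrent event (ICE1).**

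- Started in A04: it cannot have been ongoing when A02 ended, so it is never merged.
- Started in A02: a merge needs equal start dates, so the merged record keeps the same start. The censoring for the secondary estimand in Protocol 17.4.5.3 runs from initiation, not from the end date.
- Primary analysis: SAP 9.2.1.1 includes events regardless of AMX0035 use.

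The one remaining route is loss of the AMX0035 name to another carried-over drug with the same ATC2 group and start date. The documents do not show that this occurs.

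**Frequency.** A merge needs an A04 record, so the affected subjects lie among the 202 enrolled in A04 when the SAP was signed (SAP 4.2). The range from the documents alone is 0 to 202, and nothing narrows it.

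**The case against.** The strongest reply is that this is a programming detail in descriptive tables of a study that has been stopped. SAP 8.3.1.3 speaks of merging one A02 record with one A04 record and does not prescribe chaining. When both drugs continue, the correct A–A and B–B pairs also exist, and a sensible programmer would choose them. The planned outputs are subject counts, so most rows cannot change. All of this stands, and it limits the size of the point. It does not remove the point: the text gives no rule for choosing the correct pairs, and the preferred-term rows depend on that choice.

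Three stronger readings are tempting, and the documents do not support them.

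- **Shared start dates are common because of the imputation rules.** Those rules are given for deciding concomitant use. The SAP does not say that imputed dates enter the merge. Ties would become more likely only if they did.
- **ICE1 is misdated, so the secondary estimand is damaged.** The merge cannot move an AMX0035 start date, as shown above. The visible text does not derive ICE1 from coded terms, the text of SAP 9.2.1.3 is not visible, and Protocol 11.3 has AMX0035 use recorded in the CRF.
- **The September 2019 dictionary cannot code AMX0035, so it would be mixed with prohibited drugs.** Protocol 8.1, in a version of July 2022, says "The use of AMX0035 will be allowed for patients in the event that it becomes commercially available via prescription". That concerns marketing, not dictionary content, so a coding gap is plausible but not shown. SAP 8.3.1.1 also excepts AMX0035 when it counts prohibited medication as a major deviation, and those deviations are settled in a blinded review meeting.

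**Conclusion.** The point holds as a defect in the merge rule with a limited reach. For continuing drugs that share an ATC level 2 group and a start date, the rule matches different drugs to each other and leaves the surviving name undefined. The possible damage is a subject missing from a preferred-term row (or from an ATC level 4 row in the riluzole and AMX0035 tables), and a wrong end date in the integrated record. Subject counts at ATC levels 1 and 2, the primary analysis and the AMX0035 start date are not affected.

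A reader might infer that co-medication by arm is generally miscounted, or try to put a number on the subjects affected. Neither follows. The failure needs three things together (one group, one start date, both drugs carried over), and any share of the 202 entrants would be an assumption. The conclusion rests on a literal reading of SAP 8.3.1.3. A programming specification that already resolves multiple matches by drug name would answer it in practice, but neither document mentions one.

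**What to change.** In SAP 8.3.1.3:

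- Replace the ATC level 2 condition with equality of the WHO-DD preferred name, using the reported term as tie-breaker. Keep the start date condition and the two ongoing conditions. This brings the rule into line with the lowest-level-term match used for adverse events.
- State that start dates are compared as reported, before any imputation.
- State that each A02 record joins at most one A04 record, and which name the merged record carries.

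As a secondary safeguard, identify AMX0035 and riluzole from their CRF records before any merge. Confirm that the September 2019 WHO-DD version can code AMX0035, and write down the coding convention used.

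The cost is one changed condition in the merge program, a few lines of SAP text and a check of how AMX0035 was coded. No new data are needed. If the tables have already been produced, list the record pairs that match on ATC level 2 but differ in preferred name. That shows at once whether any row changes, and the outcome can be reported in the CSR as a deviation from the planned analysis.
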